4.6.3. Laboratory Safety Variables

The clinical laboratory data consists of serum chemistry, hematology, and urinalysis. Clinical laboratory values will be converted to standard international (SI) units and grouped by function in summary tables. Conventional unit may be provided. Functions are defined as follows:

Blood Chemistry: Sodium; Phosphorus; Alanine aminotransferase (ALT); Potassium; Glucose; Aspartate aminotransferase (AST); Chloride; Albumin; Total bilirubin; Bicarbonate; Creatinine; Alkaline phosphatase (ALP); Calcium; Blood urea nitrogen (BUN); Lactate dehydrogenase (LDH); Magnesium; Uric acid

Hematology: Hemoglobin; White blood cells (WBCs); Platelet count; Differential: Neutrophils, Lymphocytes, Monocytes

Urinalysis: Glucose; pH; Ketones; Blood; Specific gravity; Spot urine protein

Immune safety tests consist of rheumatoid factor (RF), thyroid-stimulating hormone (TSH), C-reactive protein (CRP), and antinuclear antibody (ANA).

4.6.4. Vital Signs

Vital signs will be collected according to Table 5, Table 6, Table 7, Table 8, and Table 9 Study Schedule of the protocol:

- Body temperature (°C)
- Resting systolic blood pressure and diastolic blood pressure (mmHg)
- Pulse (beats/minute)

- Respiratory rate (breaths/minute)

4.6.5. 12-Lead Electrocardiography (ECG)

A standard 12-lead ECG will be performed at time points according to Table 5, Table 6, Table 7, Table 8, and Table 9 of the protocol. The ECG is to be recorded in triplicate. The ECG strips or reports will be retained with the source. The ECG will be reviewed by the investigator (paper or electronic tracing) and will be available for comparison with subsequent ECGs by the investigator:

- PR Interval (msec)
- QRS Interval (msec)
- QT Interval (msec)
- Heart Rate (BPM; recorded from the ventricular rate)

Corrected QT (QTc) will be calculated from the QT interval and RR by two methods:

- Bazett's correction = $QT/[RR^{1/2}]$
- Fredericia's Correction = $QT/[RR^{1/3}]$

Any ECG finding that is judged by the investigator as a clinically significant change (worsening) compared to the baseline value will be considered an AE, recorded, and monitored.

4.6.6. Physical Examination Variables

A thorough complete or limited physical examination will be performed at visits specified in Table 5, Table 6, Table 7, Table 8, and Table 9 of the protocol. Care should be taken to examine and assess any abnormalities that may be present, as indicated by the patient's medical history.

Complete physical examination will include examination of skin, head, eyes, nose, throat, neck, joints, lungs, heart, pulse, abdomen (including liver and spleen), lymph nodes, and extremities, as well as a brief neurologic examination. Limited physical examination will include lungs, heart, abdomen, and skin.

4.7. Pharmacokinetic Variables and Immunogenicity Variables (ADA)

Serum concentration of cemiplimab will be assessed at multiple time points throughout the study treatment and follow-up periods, and descriptive PK variables will include:

- C_{trough} - pre-infusion concentration
- C_{eoi} - concentration at end-of-infusion
- t_{eoi} - time of end-of-infusion

Anti-drug antibody variables include status (positive or negative), titer, NAb status and time-point/visit. Serum samples for ADA will be collected at the clinic visits specified in the protocol.

5. STATISTICAL METHODS

For continuous variables, descriptive statistics will include the following: the number of patients reflected in the calculation (n), mean, median, standard deviation, minimum, and maximum. In addition, 25th percentile and 75th percentile will be provided.

For categorical or ordinal data, frequencies and percentages will be displayed for each category. The denominator will be determined by the analysis population used for the summary.

For time-to-event variables, median time-to-event (and the survival rate at a fixed time point) and its 95% confidence intervals will be summarized by the Kaplan-Meier method.

Statistical analysis for efficacy will be conducted independently for each group.

The data cut-off for primary efficacy analysis will be six months after the last patient starts the treatment, plus at most three additional months if a tumor response of CR or PR occurring at six months need be confirmed. The study will continue for data collection of tumor response, duration of response and safety after primary efficacy analysis. The statistical analysis of duration of response will be updated after four additional months to allow for sufficient data maturation.

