For Group 4 (cemiplimab IV Q4W): Cemiplimab IV regimen every 4 weeks (Q4W) will be assessed in Group 4. The dose of 600 mg IV Q4W is supported by modeling of cemiplimab exposure in serum and by observed data with other doses and schedules in this study and the FIH study of cemiplimab R2810-ONC-1423. While a 500 mg IV Q4W dose is predicted to provide similar cemiplimab exposure (AUC_{12W}) to that of a 3 mg/kg IV Q2W dose, a slightly higher dose is proposed to achieve cemiplimab trough concentrations (C_{trough}) during the Q4W dosing that remain between those observed at 3 mg/kg IV Q2W and at 350 mg IV Q3W. Based on this approach, a dosing regimen of 600 mg IV Q4W was selected, that is predicted to result in a steady state C_{trough} value of 59 mg/L, while C_{max} and AUC_{12W} would be slightly higher, by about 51% for C_{max} and about 29% for AUC_{12W} , than observed at a 350 mg IV Q3W dose. Previous data from the FIH study R2810-ONC-1423 demonstrate that the safety profile is flat between 3 mg/kg Q2W and 10 mg/kg Q2W. The predicted exposures and C_{max} associated with the 600 mg Q4W regimen are less than that achieved with the 10 mg/kg Q2W regimen.

For Group 5 (pilot cohort with 1 dose of cemiplimab SC): A single dose of cemiplimab 438 mg SC (actual dose is 437.5 mg), followed by cemiplimab 350 mg IV Q3W will be administered to assess the bioavailability of SC cemiplimab and to determine the SC dose regimen to be used in the cohort based on population PK approaches. As an indication, if the SC bioavailability of cemiplimab is confirmed to be around 0.7, which is generally the case for mAbs, simulated cemiplimab exposure at steady state after cemiplimab 438 mg SC Q3W would be around 54 mg/L for C_{trough} , 89 mg/L for C_{max} and 3036 mg/L*day for AUC_{12W} , compared to 53 mg/L, 157 mg/L and 6950 mg/L*d after cemiplimab 350 mg IV Q3W, respectively.

For Group 6 Option for SC cemiplimab (at or after 27 weeks): Protocol Amendment 9 will provide patients in Group 6 who have completed ≥ 27 weeks of IV cemiplinab treatment the option to receive subsequent doses as cemiplimab SC. The timing (≥ 27 weeks) corresponds to the interim and primary efficacy analyses for Group 6. PA9 will only be implemented after the data cut for the primary analyses, when all patients will have had the opportunity for at least 3 tumor assessments (≥ 27 weeks).

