3.2. Planned Interim Analysis

Interim Analysis for Group 2:

At the time of the planned efficacy analysis for Group 1 (6 months after last patient, first dose), an interim analysis of Group 2 patients will be performed in order to assess the risks and benefits of cemiplimab in unresectable locally advanced CSCC. This analysis will be restricted to Group 2 patients with potential for adequate follow-up, defined as patients who have the opportunity to receive approximately 9 months of study treatment at the time of the interim analysis. This analysis will provide an ORR (with 95% confidence interval) for Group 2 patients with adequate follow-up.

Interim Analysis for Group 6:

An interim analysis of Group 6 patients will be performed after the first 50% of patients have had the opportunity to be followed up for a minimum of 28 weeks (27 weeks for 3 tumor assessments + 1-week assessment window) or have reached the end of study.

For additional details, please see Section 9.7.

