9.5.2. Efficacy Analyses

The primary endpoint for efficacy analyses is the ORR, by central review. For Group 1 and Group 3 patients in which all response assessments are done by RECIST 1.1 (Eisenhauer 2009) analysis of radiologic scans, the independent radiology review is the central review. For Group 2 patients (and some Group 1 and Group 3 patients), response assessments include photos and radiologic scans, and the independent composite review committee will serve as the central review.

The primary analyses of efficacy are based on the binomial exact confidence interval approach, ie, whether the lower limit of 95% confidence interval will exclude a historical control ORR that is not deemed clinically meaningful. The 95% binomial exact confidence intervals using Clopper-Pearson method (Clopper 1934) for observed ORRs are listed for Groups 1 and 3 (Table 10), Group 2 (Table 11), Group 4 (Table 12), and Group 6 (Table 13).

The investigator-assessed ORR will be considered as a secondary analysis. Patients who are deemed as not evaluable according to RECIST 1.1 or inevaluable by the composite efficacy criteria will be considered as not reaching PR/CR for ORR (see Section 6.3.2).

The secondary efficacy endpoints as measured by DOR, PFS, and OS will be summarized by median and its 95% confidence interval by the Kaplan-Meier method.

The CR rate will be summarized descriptively with 95% confidence interval. Absence of residual CSCC in patients with locally advanced CSCC achieving a clinical response to cemiplimab, as measured by central review, will be summarized descriptively.

On an exploratory basis, efficacy data between different groups may be described. Such analyses should be performed so that each group has a similar amount of follow up (for example, at time of primary analysis, which is pre-specified as last patient first dose (LPFD) plus approximately 6 months for each group.)

Amendment 9: For Group 6 patients who opt to switch to SC cemiplimab, efficacy data per central review will be censored at the first SC dose. Because Group 6 patients are only allowed to switch to SC cemiplimab after completing at least 27 weeks on study (3 tumor assessments after baseline), which is the pre-specified timepoint for primary efficacy analyses in Group 6, switching to SC dosing will have no impact on the primary efficacy analysis for Group 6.

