2.3. Study Plan

After a screening period of up to 28 days, Group 1 and Group 2 patients will receive up to twelve 56-day (8-week) treatment cycles for a total of up to 96 weeks of treatment. Each patient will receive 3 mg/kg cemiplimab intravenously on days 1, 15±3, 29±3, and 43±3 during each treatment cycle. Tumor assessments will be made at the end of each treatment cycle. Extensive safety evaluations will occur on day 1 of each cycle; routine safety evaluations will be conducted at each cemiplimab dosing visit.

Group 3 patients will receive up to six 63-day (9-week) treatment cycles for up to 54 weeks of treatment. Each patient will receive 350 mg cemiplimab intravenously on days 1, 22±3, and

43 ±3 during each treatment cycle. Tumor assessments will be made at the end of each treatment cycle. Extensive safety evaluations will occur on day 1 of each cycle, with routine safety evaluations to be conducted at each cemiplimab dosing visit.

Group 4 patients will receive up to six 56-day (8-week) treatment cycles for up to 48 weeks of treatment. Each patient will receive 600 mg cemiplimab intravenously on day 1, 29±3, and 56 ±3 during each treatment cycle. Tumor assessments will be made at the end of each treatment cycle. Extensive safety evaluations will occur on day 1 of each cycle, with routine safety evaluations to be conducted at each cemiplimab dosing visit.

Group 5 patients will receive up to six 63-day (9-week) treatment cycles for up to 54 weeks of treatment. Each patient will receive 438 mg cemiplimab SC for the first dose and receive 350 mg cemiplimab intravenously on day 22±3, and 43 ±3 in cycle 1 and day 1, 22±3, and 43 ±3 during rest of treatment cycles. Tumor assessments will be made at the end of each treatment cycle. Extensive safety evaluations will occur on day 1 of each cycle, with routine safety evaluations to be conducted at each cemiplimab dosing visit.

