Group 6 patients will receive up to twelve 63-day (9-week) treatment cycles for up to 108 weeks of treatment. Each patient will receive 350 mg cemiplimab intravenously on days 1, 22±3, and 43 ±3 during each treatment cycle. Tumor assessments will be made at the end of each treatment cycle. Extensive safety evaluations will occur on day 1 of each cycle, with routine safety evaluations to be conducted at each cemiplimab dosing visit. After implementation of PA9, patients will be given the option to receive subsequent doses of cemiplimab SC. The first 12 patients who opt to switch to SC will receive cemiplimab [REDACTED]. The next ≥6 patients who opt to switch to SC will receive cemiplimab [REDACTED]. Group 6 patients will have the option to switch to SC dosing or to remain on 350 mg Q3W IV dosing.

A patient will receive treatment until the treatment period (96 weeks in Group 1 and Group 2; 54 weeks in Group 3; 48 weeks in Group 4; 54 weeks in Group 5; 108 weeks in Group 6) is complete, or until disease progression, unacceptable toxicity, withdrawal of consent, or confirmed complete response (CR). Group 1 and Group 2 patients with confirmed CR after a minimum of 48 weeks of treatment and Group 6 patients with confirmed CR after a minimum 54 weeks of treatment may elect to discontinue treatment and continue with all relevant study assessments (eg, efficacy assessments).

Groups 1 through 5: Patients in all groups who do not experience progressive disease (PD) will be followed for an additional nontreatment period of up to approximately 6 months with scans performed every 8-12 weeks. After completion of this follow-up period, patients will then enter an extended follow-up period for approximately 1 additional year with assessments every 4 months. Patients in Groups 1 to 5 who complete treatment without disease progression and subsequently experience disease progression during the follow-up period without any intervening systemic anticancer therapy, are eligible for up to 2 years of retreatment with cemiplimab 350 mg IV Q3W.

Group 6: Patients who do not experience PD at the completion of the planned treatment period will enter follow-up for approximately 6 months. There is no extended follow-up for Group 6. Patients enrolled in Group 6 are not eligible for retreatment.

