4.5. Efficacy Variable

4.5.1. Primary Efficacy Variable

Overall response is based on **central-reviewed evaluation** at each time point at which a response assessment occurs using the RECIST version 1.1 (Appendix 1 of the protocol) or the composite response criteria (Appendix 2 of the protocol).

Best overall response (BOR) is determined once all the overall response data for the patient are known. The best overall response is the best response recorded during the study.

- Best overall response of CR or PR must be confirmed by consecutive evaluations of overall response of CR or PR at time points at least 4 weeks apart. In addition, locally advanced CSCC patients followed by digital medical photography require biopsy to confirm CR.
- Best overall response of SD must have met the response SD criteria at least once ≥ 39 days (6 weeks*7 days/week -3 days) after start of study treatment. Best overall

response of (early) PD does not require confirmation using the RECIST or the composite response criteria.

- The best overall response for patients who do not have any post-baseline tumor assessment will be not evaluable (NE). Patients with best overall response of NE will be considered as not reaching an objective response of CR or PR.

Objective response rate (ORR) is determined by the proportion of patients with best overall response of CR or PR in the FAS by group.

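### The SAP's six-month primary cut-off conflicts with the 27-week, three-assessment timepoint both documents give for Group 6, and it moves only when a response is awaiting confirmation

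*SAP*

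**What the plan says.** **SAP section 5** gives a single cut-off for all groups: "The data cut-off for primary efficacy analysis will be six months after the last patient starts the treatment, plus at most three additional months", the added time applying "if a tumor response of CR or PR occurring at six months need be confirmed".

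**Schedule.** SAP 2.3: "Group 6 patients will receive up to twelve 63-day (9-week) treatment cycles for up to 108 weeks of treatment", with tumor assessments at the end of each cycle. Protocol Table 7 puts that visit at day 63 ± 3.

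**Group 6 primary timepoint.** Protocol 9.5.2 and SAP 5.8.1 describe at least 27 weeks on study, with three post-baseline assessments, as the point "which is the pre-specified timepoint for primary efficacy analyses in Group 6". Protocol 1.2.1 describes the Group 6 primary data cut as the time "when all patients will have had the opportunity for at least 3 tumor assessments". Protocol 9.5.2 also gives last patient first dose plus approximately six months for each group.

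**Group 6 interim.** Protocol 3.2 requires "a minimum of 28 weeks (27 weeks for 3 tumor assessments + 1-week assessment window"; protocol 9.7 and SAP section 8 repeat this.

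**Confirmation.** For a CR or PR to count as a patient's best response, SAP 4.5.1 says it "must be confirmed by consecutive evaluations of overall response of CR or PR at time points at least 4 weeks apart".

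**The concern.** Two features of the SAP section 5 rule cause trouble for Group 6.

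1. **Timing.** A programmer who follows section 5 literally will cut the data before the last enrollees reach their third assessment. One who follows 5.8.1 will not. The protocol's statement that switching to subcutaneous dosing leaves the primary analysis untouched rests on the 27-week timepoint, not on six months.

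2. **Trigger.** The only written reason to move the cut-off is a favourable result that is still unconfirmed. The text does not say whether investigator or central assessment triggers the move, how long it lasts within the three-month ceiling, or whether other patients' first responses seen in that time count. Conversely, a late enrollee whose first response would appear at week 27 triggers nothing.

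The stake is the primary test, whether the confirmed ORR excludes 28%, in an open-label study where the pass mark can turn on one patient.

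**Working it through.** **Inputs.** Cycle length 63 days, assessment window ± 3 days, confirmation at least 4 weeks later, interim minimum 28 weeks, N = 167, null 28%, alternative 40% (SAP 2.2, 2.3, 4.5.1 and 8; protocol 9.2 and Table 7). Six months is 181 to 184 days, mean 182.6. Accrual time is not given, so 12 to 24 months with uniform entry is assumed.

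**The plan's own figures.** 27 weeks + 1 week = 28 weeks, as stated for the interim. With Clopper-Pearson 95% limits, 59/167 (35.3%) has a lower limit of 28.1% and 58/167 has 27.5%, as in protocol Table 13. The exact probability of at least 59 responders is 2.3% at a true ORR of 28% and 90.6% at 40%.

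**Calendar, counted from the last patient's first dose**

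| Event | Day | Relative to six months (182.6) |
|---|---|---|
| Assessment 2 | 126 ± 3 | before |
| Assessment 3 = 3 × 63 | 189 (186–192) | 6.4 days after |
| Interim minimum = 28 × 7 | 196 | 13.4 days after |
| Assessment 4 = 4 × 63 | 252 (249–255) | late edge 72.4 days after |
| Six + three months | about 274 | 91 days after |

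Even the early edge of assessment 3 (day 186) misses the cut-off. It fits only if all three cycles are compressed to the 60-day minimum spacing in Table 7 (3 × 60 = day 180). For 56-day cycles assessment 3 is at 3 × 56 = day 168 (165–171), which is inside six months.

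**Patients affected.** Number starting within g days of the last patient ≈ 1 + 166 × g / accrual days.
- g = 6.4 (nominal date): 1 + 166 × 6.4/365.25 = 3.9, and 1 + 166 × 6.4/730.5 = 2.4, so about 2 to 4.
- g = 9.4 (late edge, day 192): 5.3 and 3.1.

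**Effect on the test.** Let k late patients respond with probability 0.40 × (1 − f) and the other 167 − k with probability 0.40. Power is the chance of at least 59 responders in total. The loss fraction f is an assumption.

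| k | f | Expected ORR | Power |
|---|---|---|---|
| 0 | – | 40.0% | 90.6% |
| 2 | 10% | 39.95% | 90.4% |
| 4 | 30% | 39.7% | 89.3% |
| 4 | 100% (extreme) | 39.0% | 85.8% |

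**Sensitivity to one responder.** At a true ORR of 28%, the chance of at least 58 responders is 3.4%, against 2.3% for at least 59. If a moved cut-off always admitted one further responder (an illustration, not an estimate), the one-sided error would go from 2.3% to 3.4%.

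**The case against.** The strongest reply is that this is loose wording over about 6 days. Each document also carries the 27-week statement specifically for Group 6, and protocol 9.5.2 says only approximately six months. The early-cut loss lowers ORR, which is conservative. The extension is tied to confirming a response around six months. Longer follow-up also moves closer to the endpoint in protocol 8.2.1, which counts response over 12 cycles. Most of this stands: the size is small and the direction of the early-cut loss is safe. It does not remove the contradiction, because the cut-off sentence makes no exception for Group 6 and no text says which statement governs.

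Stronger readings that a reader might infer, and that the documents do not support:

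- **Group 3 follow-up is also too short.** Group 3 has 63-day cycles too, but no passage requires three assessments by its primary cut.
- **The extension inflates ORR.** The SAP is silent on whether new first responses count during the added time. If it serves only to confirm responses already seen, the dependence on outcome is mild.
- **Everyone starting in the last 72 days is at risk** (about 16 to 33 patients: 167 × 72/730 to 167 × 72/365). All but the last 2 to 4 have the nominal week-27 scan before the cut, and a new response there is what the extension exists to confirm. If 5% of patients first respond at week 27 (assumed), the uncovered patients contribute 0.1 to 0.2 responders (2 to 4 × 0.05).
- **The last enrollees can be confirmed only by responding at week 9 and again at week 18.** Confirmation needs only 4 weeks, so a day-126 response could be confirmed from day 154.

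**Conclusion.** The point holds for Group 6. SAP section 5 contradicts SAP 5.8.1 and protocol 9.5.2 and 1.2.1, and gives the final analysis about 13 days less minimum follow-up than its own interim. As written, the cut-off can also depend on outcome. The numerical effect is small: about 2 to 4 of 167 patients miss assessment 3, if accrual is uniform over 12 to 24 months and visits are at nominal dates. Power falls from 90.6% to about 89–90% if those patients lose 10–30% of their responses. The reason to settle it is that 59 responders pass and 58 fail, so the rule should not be open to choice once responses are known. Neither an upward bias nor a deficiency in Group 3 or the 8-week-cycle groups is shown.

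**What to change.** In SAP section 5 and protocol 9.5.2, state the same rule for Group 6:

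- The primary cut-off is 28 weeks after the last patient's first dose, matching the interim.
- A fixed confirmation period follows, whatever responses have been seen, through the week-36 assessment and its window (day 255 after the last patient's first dose). This is inside the nine months already allowed and replaces the conditional extension.
- That period serves only to confirm responses first seen by the cut-off. Later first responses are reported in the updated analysis.

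Protocol 1.2.1 places Amendment 9 after the Group 6 primary data cut, and SAP 1.2.5 bases this SAP on Amendment 9, so the cut may already have been taken. If so, document its actual date and whether the extension was used, and report ORR under the fixed rule as a sensitivity analysis.

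**Cost.** Wording in two documents, and a Group 6 data cut always about 10 weeks later than six months (255 − 182.6 = 72 days). First responses after the cut-off would not count in the primary analysis even though protocol 8.2.1 counts response over 12 cycles, so the text should say so openly. The 8-week-cycle groups need no change.
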